## Exploratory analysis

In an exploratory way, in order to study the temporal evolution of geriatric and quality of life scores (Spitzer QoL Index, IADL, ...), mixed models of analysis of variance for repeated measures of each of the scores will be performed.

## 12. ANCILLARY STUDY

During this study, copies of the evaluation images will be collected for each patient. It is planned to look for predictive markers of response and progression-free survival under regorafenib treatment.

- Fat is now considered as an endocrine and paracrine organ (29). Today we distinguish 2 types of fat, visceral and subcutaneous, because they have a different secretion profile (30). Visceral fat secretes adipokines, some of which are pro-angiogenic and proliferative. Cross-sectional imaging (CT/MRI) is the only technique to separate visceral fat from subcutaneous fat. It has been hypothesized that pro-angiogenic adipokines secreted by visceral fat may influence the response and survival of patients treated with anti-angiogenic drugs. As an exploratory study, a monocentric study of 120 patients treated in 1st line metastatic colorectal cancer was performed: 80 patients were treated with bevacizumab + chemotherapy and 40 patients with chemotherapy alone (31). It is clear that patients treated with bevacizumab with high visceral fat have a poorer 2-month response, shorter progression-free survival and overall survival.

Other studies of the same type are underway for other cancers and the preliminary results confirm these initial results. The major objective will be to validate that visceral fat area (calculated on the baseline scan) is an independent predictor of response at the first assessment (8-week scan) and of progression-free survival.

- In addition, an exploratory study of tumor density will be conducted based on the analysis of baseline and 8-week scans.

Three tumor density measurements will be performed for a maximum of 2 targets per organ, on axial slices made after injection of iodinated contrast. For each target, a density measurement by a global region of interest will be performed on the slice showing the largest tumor surface. A density measurement will be performed on the tumor area appearing the most hyperdense. Finally, a measurement will be performed on the most hypodense tumor area. Finally, a density measurement of the underlying healthy organ will also be noted for each scan. The injection time (arterial, portal or late) will be noted for each target, as well as the quantity of contrast medium used (noted on the radiological report). These measurements will be repeated on the 8-week scan.

The objective will be to determine, with the help of ROC curves, the threshold of variation of the tumor density allowing to predict the response and the progression.

- Finally, sarcopenia has been shown to be a predictive factor for toxicity of chemotherapy in colorectal cancers (32) and also of sorafenib (another tyrosine kinase inhibitor close to regorafenib) in hepatocellular carcinoma (33). Sarcopenia will be analyzed on abdominal sections to investigate its predictive value of toxicity and efficacy of regorafenib.

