### 2.2 Secondary Objectives

Evaluate:

- Overall survival at 1 year
- Progression-free survival at 1 year
- Tumor control rate at 2 months (centralized review)
- Objective response rate assessed from the best response under treatment
- Time to therapeutic failure
- Time to degradation of autonomy
- Time to degradation of quality of life
- Geriatric prognostic and predictive parameters
- Dose-intensity and its correlation with tumor control rate
- Tolerance of regorafenib according to the NCI-CTC AE version 4.0 scale

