## 8. PATIENT MONITORING

### 8.1 during treatment :

- Clinical examination: weight, height, BP, collection of toxicities and clinical tumor assessment

- Cycle 1 and 2: at D1, D7 and D14
- Cycles 3 and following: at D1 of each cycle
- At the end of treatment visit

The ECOG is completed on Day 1 of each cycle (cycle 1 and following) and at the end-of-treatment visit.

- Bioassay:

At each cycle: at D1 and D14; (for cycle 1, the biological test at D1 can be the inclusion test, if it is less than 14 days old).

The assessment at Day 1: CBC-platelets, natraemia, kalemia, calcemia, magnesemia, phosphoremia, uricemia, creatininemia, creatinine clearance, albuminemia, ASAT, ALAT, PAL, total and conjugated bilirubinemia, GGT, TP, TSH, lipase, INR for patients treated with AVK.

Assessment at D14: CBC/blood platelets, creatinine clearance, natraemia, kalemia, creatinine, ASAT, ALAT, PAL, total and conjugated bilirubin, GGT, INR for patients treated with AVK.

- At the end-of-treatment visit: CBC/blood platelet count, natraemia, kalemia, creatinine, creatinine clearance, AST, ALT, PAL, total and conjugated bilirubin, GGT

A coagulation test should be performed at D1 and D14 of each cycle, if patients are treated with anticoagulant. If the values are outside the therapeutic range, the dose of anticoagulant should be modified and a coagulation test should be performed every week until stabilization.

- Other follow-up:

During treatment, an ECG will be performed if deemed useful by the investigator.

Every 4 weeks, until progression, CEA measurement will be performed as well as quality of life and geriatric parameters assessment.

Every 8 weeks, until progression, a thoraco-abdomino-pelvic scan will be performed to evaluate the tumor response.

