1.1.3 Exploratory studies

The objective is to search for predictive factors of response and progression-free survival under regorafenib treatment. An analysis of the evolution of geriatric parameters during the follow-up will also be performed. Plan experimental

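### The exploratory tumour-density cut-off rests on a week-8 measurement, with no week-8 landmark and no stated correction for optimism

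*Protocol*

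**What the plan says.** Protocol section 12 states that "an exploratory study of tumor density will be conducted based on the analysis of baseline and 8-week scans". Three densities are taken per target (whole lesion, brightest area, darkest area), and "These measurements will be repeated on the 8-week scan". ROC curves are then to give "the threshold of variation of the tumor density allowing to predict the response and the progression". The text does not define that response or that progression, and it does not say which of the three densities is used.

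The timing of outcomes comes from elsewhere:
- Protocol 8.1: "Every 8 weeks, until progression, a thoraco-abdomino-pelvic scan will be performed to evaluate the tumor response".
- Protocol 11.1 reads the primary endpoint 2 months after treatment starts, takes objective response as the best over all evaluations, and counts PFS from inclusion.
- The visceral-fat objective in section 12 speaks of an "independent predictor of response at the first assessment (8-week scan) and of progression-free survival".

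SAP 1.1.3 repeats the general aim to "search for predictive factors of response and progression-free survival under regorafenib treatment". SAP 4.6 names only geriatric parameters as the factors to be studied. It contains no density analysis, ROC method, landmark or validation step.

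**The concern.** Prediction needs a marker that is known before the outcome. A change that is complete only at week 8 cannot come before a response or progression read on the week-8 scan. It could come before later events, but the plan sets no week-8 starting point for them. If PFS from inclusion is used, patients who die or leave before the scan have no value, so the analysis is conditional on having been scanned.

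The second problem is the cut-off. A ROC threshold picked in a small sample looks better in that sample than it will in new patients. With no correction stated, the reported threshold could pass into later work with an inflated accuracy. The study's conclusion about density as an early marker is what is at stake.

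**Working it through.** **The plan's own figure.** The density study has no sample size of its own; it inherits the trial's 42. That number reproduces. With X ~ Bin(42, p) and success at 16 or more, P(X ≥ 16 | 0.25) = 0.0416 and P(X ≥ 16 | 0.47) = 0.9057. This is the smallest exact design with one-sided alpha ≤ 5% and power ≥ 90%.

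**Timing.** Density change = value at week 8 minus value at baseline, available at week 8.

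| Possible outcome | When it is known | Relation to the marker |
|---|---|---|
| Response or progression on the 8-week scan | Week 8 | Concurrent |
| Best response or progression after week 8 | Later | Can be predicted, from a week-8 landmark |
| PFS from inclusion | From inclusion onward | Includes time before the marker exists; analysable only in scanned patients |

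**Size of the optimism.** Inputs: N = 42 and the expected control rate of 47% (Protocol 11.3). 0.47 × 42 = 19.7, so 20 patients with control and 22 without. It is assumed that all 42 have a density value and that the marker is normally distributed. The Youden index is J = sensitivity + specificity − 1. In each simulated trial the cut-off that maximises J is chosen and judged in the same patients.

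Marker with no signal (true J = 0), 20 versus 22:
- Direction fixed in advance: mean apparent J = 0.17, 95th percentile 0.35.
- Direction left free: mean apparent J = 0.25, 95th percentile 0.40.
- Best of three measures, direction free: mean about 0.32. This treats the three as independent. Real ones would be correlated, so it is an upper illustration.

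Because the outcome is undefined, the split between groups is also uncertain. With direction fixed and N = 42, for assumed event rates:

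| Event rate | No signal: apparent J | True AUC 0.70: apparent J | Same cut-off in new patients |
|---|---|---|---|
| 47% | 0.17 | 0.41 | 0.26 |
| 25% | 0.20 | 0.44 | 0.25 |
| 10% | 0.29 | 0.51 | 0.24 |
| 5% | 0.34 | 0.55 | 0.23 |

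At AUC 0.70 the overstatement runs from 0.41 − 0.26 = 0.15 to 0.55 − 0.23 = 0.32. The central 95% range of the fitted cut-off is about 2.1 marker standard deviations wide at a 47% rate, and 2.8 at 10%.

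**Precision of the AUC (Hanley–McNeil).** Assumed A = 0.70, n1 = 20, n2 = 22.
- A/(2 − A) = 0.7/1.3 = 0.5385; 2A²/(1 + A) = 0.98/1.7 = 0.5765; A² = 0.49.
- Variance = [0.21 + 19 × 0.0485 + 21 × 0.0865]/(20 × 22) = 2.947/440 = 0.0067.
- SE = 0.082; 1.96 × 0.082 = 0.16, so about 0.54 to 0.86.

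**The case against.** The protocol calls the density work exploratory, and no endpoint, decision rule or treatment decision uses it. The density text does not say that its response is the one read at week 8; those words belong to the visceral-fat objective. Later scans continue, so later response and progression could be predicted from a week-8 change. Validation is neither described nor excluded. All of this stands, and it limits the point to a request for a better-defined analysis.

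A reader might infer four stronger things that the documents do not support:
- **That the threshold would be false.** The simulations show bias and instability. They do not show that any cut-off found must be wrong.
- **That nothing is predicted.** This holds only for an outcome read on the same scan, and the outcome is left open.
- **That PFS would suffer classic immortal-time bias.** Patients above and below the cut-off must both reach the scan, so, apart from any earlier clinical progression, they share the same lead-in. The problem is mainly selection on having been scanned. Nor does the text specify a density model for PFS from inclusion.
- **That predictive wording must be removed throughout.** Visceral fat is a baseline marker, so the timing problem does not reach it, even though the aim there is to "validate that visceral fat area" as an independent predictor. The secondary objective reads "Geriatric prognostic and predictive parameters", and Protocol 11.4 and SAP 4.6.1 already call the geriatric factors prognostic. Predictive can also be read as forecasting outcome in treated patients. The rest is largely terminology.

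The figure of 0.25 needs its condition stated: it applies when direction is left free. The plan fixes none, but 0.17 is the fair figure once one is fixed.

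**Conclusion.** The point holds as an inexpensive improvement to an exploratory analysis. For response or progression on the 8-week scan, density change is concurrent with the outcome. For PFS from inclusion, the analysis would be restricted to patients who reached the scan. As written, the cut-off would be optimistic and imprecise: mean apparent J of 0.17 (direction fixed) or 0.25 (direction free) for a marker with no signal, and about ±0.16 on an assumed AUC of 0.70.

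These sizes assume a 20 versus 22 split, a normal marker and a density value for all 42 patients. Missing 8-week scans would make both problems worse. That the cut-off would be judged in the same patients is inferred from the absence of any validation step. With one arm, the result can describe an association among treated patients and cannot show differential benefit from regorafenib. The trial's primary and secondary endpoints are untouched.

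**What to change.** Add a short density section to the SAP:
1. Define the outcome. For progression, start the clock at the week-8 scan (landmark), in patients alive and progression-free then, with subsequent PFS as the outcome.
2. Report density change against week-8 response as a concurrent association only.
3. Pre-specify one of the three density measures and the direction expected to be favourable.
4. Report the cut-off, sensitivity, specificity and AUC with bootstrap optimism correction and confidence intervals. Repeat the cut-off search inside each bootstrap sample.
5. Describe the density result as an exploratory association within treated patients.

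The cost is analysis text and a bootstrap run; no new data or patients are needed. The price is a smaller landmark set, about 20 patients if the assumed 47% control rate holds (0.47 × 42 = 19.7), with wider intervals and a more modest claim.

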## 13. STUDY COMMITTEES

### 13.1 Board of Directors

A steering committee will be established, chaired by the lead coordinator. This committee will include the protocol writing committee, the FFCD president, the project manager and the statistician.

### 13.2 Independent Data Review Committee

An independent monitoring committee will be established, including a physician specializing in oncogeriatrics, a gastroenterologist/oncologist, a statistician and a pharmacovigilance expert. Their functions will be described in the charter of the independent monitoring committee. It will analyze all safety data during the study. It will meet 3 months after the inclusion of the fifteenth patient. In case of unexpected toxicity, unacceptable the independent committee may recommend:

- A protocol amendment that could significantly improve treatment tolerability
- Premature termination of the study if the treatment causes intolerable side effects.

### 13.3 Centralized proofreading

A panel of radiologists will be responsible for centralized review of radiological imaging collected during the study to determine treatment responses and progressions.

## 15. ADMINISTRATIVE CONSIDERATIONS

### **Study sponsor**

The sponsor of the study is the Fédération Francophone de Cancérologie Digestive (FFCD). The study was registered under the EudraCT number: 2015-002086-29.

### **Reminder of the texts in force**

This test will be conducted according to the French law in force

### **Liability Insurance**

Insurance has been taken out by the promoter with SHAM (Société Hospitalière d'Assurances Mutuelles) under contract number XXX (Appendix 11), in accordance with Article L 1121-10 of the Public Health Code.

### **Request for authorization to the CPP and ANSM**

This protocol received the favorable opinion of the CPP (Committee for the Protection of Persons) Ile de France VIII, on 29/06/2015 (Appendix 12).

This protocol has been authorized by the ANSM (Agence Nationale de Sécurité du Médicament) (Appendix 13).

### **Collection of the patient's consent**

The investigator undertakes to collect, after information, the clinical consent of the patient in writing (information sheet and consent form in Appendix 1). A copy of these consents must be kept by the investigator for 15 years, to be presented to the supervisory authorities in case of inspection. The original should be given to the patient.

In accordance with the recommendations of the Cancer Plan (Measure 4.3.), this document has been submitted for review, advice and guidance to the Patients' Committee for Clinical Research (PCCR) of the National League Against Cancer.

### **Hospital management information and research agreement**

Prior to the implementation of the study, the hospital management will be informed by the sponsor of the investigator's interest in participating in this trial.

A research agreement will be established between the administrator of the investigating center and the sponsor.

### **Data archiving**

The files will remain confidential and can only be consulted under the responsibility of the doctors in charge of the patients. The sponsor and the health authorities in case of inspection will have direct access to these documents.

At the end of the trial, the observation book will be kept for 15 years by the investigator.

### **Computer support**

In accordance with the text of the law n° 78-17 of January 6, 1978 modified by the law of August 9, 2004, relating to data processing, files and freedoms, the data of the trial will be recorded in a computerized database of the FFCD Randomization and Analysis Management Center, excluding elements relating to the identity of patients. The FFCD has made a simplified declaration (MR01) to the CNIL for the implementation of its centralized databases.

### **Data processing**

The FFCD's Center for Randomization, Management and Analysis (CRGA) will be responsible for data management and analysis.

### **Monitoring, quality assurance and inspections by authorities**

The investigator agrees in advance that the records of the patients included in the study may be consulted by an FFCD CRA or a person mandated by the sponsor or the FFCD and/or by the health authorities to carry out an audit. On-site visits of the files, scheduled after agreement of the investigator, will take place during the protocol period of the study.

## **16. PUBLICATION RULES**

They shall be in accordance with those established by the FFCD (Appendix 10).

## **17. APPENDICES**

[ANNEXE 1 : Notice d'information et formulaire de consentement éclairé pour l'étude clinique](#)

[APPENDIX 2: "Patient" self-questionnaire](#)

[APPENDIX 3: "Team" Questionnaire](#)

[APPENDIX 4: RECIST 1.1 Criteria](#)

[APPENDIX 5: ECOG](#)

[APPENDIX 6: Measurement of creatinine clearance using the Cockcroft and Gault formula](#)

[APPENDIX 7: NCI-CTC Toxicity Criteria Version 4.0](#)

[APPENDIX 8: Regorafenib CPR](#)

[APPENDIX 9: RSI form](#)

[APPENDIX 10: FFCD Publication Rules](#)

[SCHEDULE 11: Certificate of Insurance](#)

[APPENDIX 12: Favourable opinion of the PPC](#)

[APPENDIX 13: Authorization from the ANSM](#)

1.1 Objectives

1.1.1 Main objective

The primary objective of this study is to evaluate the tumor control rate (defined as the number of patients without progression, i.e., with complete response, partial response, or stability) under regorafenib treatment, according to the investigator (RECIST v1.1), 2 months after the start of treatment.

1.1.2 Secondary objectives

Secondary objectives are :

- 1-year Overall Survival
- 1-year Progression-Free survival
- Disease control at 2 months (centralized review)
- Objective response evaluated according to best response under treatment
- Time to therapeutic failure
- Time to autonomy degradation
- Time to quality of life deterioration
- Geriatric prognostic and predictive parameters
- Dose-intensity and its correlation to disease control
- Safety of regorafenib (NCI-CTC AE version 4.0)

1.1.3 Exploratory studies

The objective is to search for predictive factors of response and progression-free survival under regorafenib treatment. An analysis of the evolution of geriatric parameters during the follow-up will also be performed. Plan experimental

1.2 Study design

Phase II open-labelled study , multicenter

1.3 Treatment

The dose of regorafenib is 160 mg (4 x 40 mg tablets) taken orally daily (21 days of treatment and 7 days without treatment, i.e. 28-day cycles).

1.4 Sample Size calculation

Clinical hypotheses are based on data from the CORRECT study and are as follows:

H₀: A tumor control rate at 2 months after the start of treatment of 25% or less is not sufficient.

H₁: A tumor control rate at 2 months after the start of treatment of more than 25% is considered sufficient. A rate of 47% is expected.

With a one-sided risk α of 5% and power of 90%, 42 patients are needed.

Patients who stop the study before documented tumor progression at 2 months will be considered non-responders for the primary endpoint analysis.

The decision rules after inclusion of 42 patients are:

- If 15 or fewer patients have a complete or partial response or stability then the treatment will be considered non-effective.
- If 16 or more patients have a complete or partial response or are stable, then the treatment will be considered effective.

1.5 Analyses planning

Analyses will be done once

1.6 Adjustments

Adjustments may be made to this analyses plan in the event of amendments to the protocol, or if phenomena not initially foreseen require statistical adaptations. In all cases, these modifications must be made before the database is frozen.

2 Study populations

2.1 Analyses populations

2.1.1 Intent-to-treat population (ITT)

The intention-to-treat population is defined as all patients included in the study, regardless of eligibility criteria.

2.1.2 Modified Intent-to-treat population (ITT_m)

The modified intention-to-treat population is defined as all patients included in the study who received at least one regorafenib tablet and had at least one imaging assessment under protocol treatment.

2.1.3 Safety population (PT)

The safety population is defined as all patients included in the study who received at least one regorafenib tablet.

3 Statistical Generalities

Analyses will be done by CRGA.

3.1 Software

Statistical analyses will be performed with SAS software version 9.4. Some graphs can be made with R software version 2.11 or later.

3.2 Conventions

Time since inclusion will be defined as the time elapsed since the day of inclusion, with the day of inclusion being considered as day 1.

Therefore, the durations will be calculated according to the following rule, e.g. for the time from death to inclusion: day of death - day of inclusion + 1.

The day before the day of inclusion (resp. the day before the day of treatment) will be considered as day -1 (day 0 does not exist).

The date of last news will be the date of the last examination performed or the last treatment or the last medical consultation/visit.

The following conversion rules will be used for the conversion of the number of days to months or years: 1 month = 30.4375 days; 1 year = 365.25 days.

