## EXAMINATION AND FOLLOW-UP SCHEDULE

	Before inclusion			During treatment (until progression)					After treatment
	J -21	J -14	J -7	C1 : D1, D7 and D14 C2 : D1, D7 and D14	D1 of each cycle (every 4 weeks)	D14 of each cycle	Every 8 weeks after the start of treatment	End of treatment visit	Every 8 weeks
Informed consent	X								
Clinical examination		X		X	X		X	X	X
Weight, height, BP		X		X	X		X	X	
ECOG		X			X		X	X	X
Geriatric questionnaires, quality of life		X			X		X		
Biological check-up 1 			X		X		X		
Biological check-up 2 						X		X	
Urine dipstick ± 24h proteinuria		X			X		X		
ECG		X			X 				
Thoracic and abdominal-pelvic CT	X						X		
ACE			X		X		X		
Cardiac ultrasound or myocardial scintigraphy ± cardiological opinion in case of cardiopathy 	X								
Assessment of treatment toxicity				X	X		X	X	

Biological check-up 1: CBC-PQ, natraemia, kalemia, calcemia, magnesemia, phosphoremia, uricemia, creatininemia, albuminemia, ASAT, ALAT, PAL, total and conjugated bilirubinemia, GGT, TP, TSH, lipase, INR for patients treated with AVK.

Biological check-up 2: CBC-Pq, natraemia, kalemia, creatinine, creatinine clearance, ASAT, ALAT, PAL, total and conjugated bilirubin, GGT INR for patients treated with AVK.

 For patients treated with an anti-coagulant, a coagulation test should be performed, if the values are outside the therapeutic range the dose of anticoagulant should be modified and a coagulation check should be done every week until stabilization.

 During treatment, an ECG will be done according to the investigator's choice.

 In case of heart disease, cardiac echography or myocardial scintigraphy, completed by a cardiologist's opinion if necessary, **dated less than 3 months before inclusion.**

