### 7.1 Duration of treatment

Causes of discontinuation are:

- progress
- occurrence of a second cancer
- Dose reduction of more than 2 times 40 mg
- interruption of treatment for more than 4 consecutive weeks
- patient refusal
- withdrawal of consent
- continuation of the study deleterious to the patient according to the investigator

Patients who discontinue study treatment will be managed according to local guidelines. The administration of any other anti-cancer treatment will be collected in the observation booklet at a follow-up visit.

Patients will be followed every 2 months after discontinuation of treatment, regardless of the reason for discontinuation, until death except for patients who have withdrawn their consent.

Patients who stopped treatment before progression will be followed to assess the date of first progression.

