## **8.2 After treatment :**

- If treatment is stopped for progression: the patient will be followed up approximately every 8 weeks to collect survival data and subsequent anti-cancer treatments.

- if the treatment is stopped for another reason: the patient will be followed every 8 weeks with a thoraco-abdomino-pelvic scanner, until progression. Then he will be followed approximately every 8 weeks to collect survival data and subsequent anti-cancer treatments.

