#### 2) Secondary criteria

The **secondary endpoints** are defined as follows:

- Overall treatment **tolerance** will be assessed by the rate of observed toxicities, graded according to NCI-CTC v4.

- **Overall survival is** defined as the time from the date of inclusion to the date of death from any cause. Patients lost to follow-up or alive at the time of analysis will be censored at the date of last report. A minimum follow-up of 1 year for the last included patient is required.

- **The tumor control rate** assessed in centralized review is defined as the percentage of patients with complete tumor response, partial tumor response, or tumor stability on regorafenib therapy 2 months after the start of therapy (RECIST criteria V1.1).

- **The objective response rate is** defined as the occurrence of at least one complete or partial response assessed from the best response (according to RECIST v1.1 criteria) during the treatment evaluations (Appendix 4). Patients who discontinue the study without response assessment will be considered non-responders.

- **Time to treatment failure is** defined as the time from the date of inclusion to the date of treatment discontinuation (regardless of cause) or death (regardless of cause). Living patients without treatment discontinuation will be censored at the date of last treatment administration.

- **Progression-free survival is** defined as the time from the date of inclusion to the date of first investigator-rated progression (clinical or radiological) or death (from any cause). Patients alive without progression will be censored at the date of last news. A minimum

follow-up of 1 year for the last included patient is required.

- **The regorafenib dose intensity** will be calculated during the first 2 cycles of treatment **and over the** entire treatment period. The theoretical dose intensity (TDI) (mg/cycle) is 3360 mg ((160mg/d x 21d ). The dose intensity (DI) actually received is equal to the total dose received divided by the total duration of treatment. The relative dose intensity (DIR) is equal to DI / DIT.

- **Time to deterioration in independence** is defined as the time from the date of inclusion to the date on which the IADL score (Appendix 2) has decreased by at least 1 point from the score calculated at inclusion. Patients alive or deceased without deterioration of autonomy will be censored at the date of last IADL assessment or the date of death.

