4.4 Secondary efficacy criteria

4.4.1 Overall Survival

4.4.1.1 Definition

It is defined as the time interval between the date of inclusion and the date of death (regardless of cause).

Patients lost to follow-up or alive at the time of analysis will be censored at the date of last news. A minimum follow-up of 1 year for the last included patient is required.

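### The SAP's date of last news counts only clinical contacts, which can bias overall survival downward if some patients are followed after progression without a visit

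*SAP*

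**What the plan says.** SAP 3.2 defines the date used for censoring: "The date of last news will be the date of the last examination performed or the last treatment or the last medical consultation/visit". No other evidence that a patient is alive is listed.

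SAP 4.4.1.1 applies it to OS: "Patients lost to follow-up or alive at the time of analysis will be censored at the date of last news". The event is death from any cause, dated at death, with no limit on how the death becomes known. The same section adds: "A minimum follow-up of 1 year for the last included patient is required". SAP 4.2.1 uses the same date for follow-up time, and SAP 4.4.5.1 uses it for progression-free survival (PFS). SAP 4.4.1.2 reports Kaplan-Meier OS at 3, 6, 9, 12 and 18 months.

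Protocol 11.1 has the parallel OS rule, with a term that it does not define: "Patients lost to follow-up or alive at the time of analysis will be censored at the date of last report".

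Three places in the protocol describe contact after treatment:
- Section 7.1: "Patients will be followed every 2 months after discontinuation of treatment, regardless of the reason for discontinuation, until death", except for patients who withdraw consent.
- The examination and follow-up schedule marks "Clinical examination" and ECOG every 8 weeks after treatment.
- Section 8.2, for patients who stop because of progression: "the patient will be followed up approximately every 8 weeks to collect survival data and subsequent anti-cancer treatments". It does not say whether this is a visit.

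**The concern.** The rule treats survivors and deaths differently. Whether a patient has died is judged with everything known at the time of analysis, but a survivor's time is moved back to the last clinical contact. Take a patient last seen at month 4 and confirmed alive by telephone at month 13: that patient leaves the risk set at month 4. A patient last seen at month 4 whose death at month 9 was reported by telephone stays at risk to month 9 and counts as an event. Time at risk is removed only from those who did well, so the censoring is informative and the estimate can move only down.

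One-year OS is a named secondary objective, and this is a single-arm trial, so no comparator carries the same error. Follow-up time would be understated by the same mechanism.

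**Working it through.** **1. What can be reproduced.** The documents give no expected OS, no target precision and no share of patients followed without visits. There is therefore no stated OS figure to reproduce. The one calculated design figure does reproduce: 42 patients with success at 16 or more gives, by exact binomial, a type I error of 0.042 at 25% and power of 0.906 at 47%. It concerns 2-month tumour control and does not use the date of last news.

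**2. Inputs from the documents.** n = 42 (SAP 1.4). Accrual is 2 per month (Protocol 11.3), so 42/2 = 21 months. Analysis is taken at 12 months after the last inclusion, the stated minimum. Potential follow-up then runs from 12 to 12 + 21 = 33 months.

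**3. Assumptions not in the documents.** Exponential OS with median m of 6.5 or 9 months. A share q of patients whose later contacts are all non-visit. Last clinical contact at month 4 for that share. All deaths known.

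**4. If the scheduled visits are kept.** Eight weeks is 56/30.4375 = 1.84 months. A survivor is then censored at most 1.84 months before the cut-off. Only patients with potential follow-up under 12 + 1.84 = 13.84 months can be censored before month 12. That is at most 1.84 × 2 ≈ 3.7 patients, none censored before 12 − 1.84 = 10.16 months. Simulation puts the 12-month bias at about 0.1 to 0.2 point and the 18-month bias at about 0.6 to 0.7 point.

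**5. If a share q has only non-visit contact later on.** Let S(t) = 0.5^(t/m).
- Alive at month t: N(t) = 42 × S(t).
- Alive at analysis, averaging S over follow-up of 12 to 33 months: A = 42 × [m/(21 ln 2)] × [S(12) − S(33)].
- Survivors moved back to month 4: k = qA.
- Kaplan-Meier at 12 months under the SAP rule: [N(4)/42] × [N(12) − k]/[N(4) − k].

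For m = 6.5: N(4) = 27.4, N(12) = 11.7, and A = 2 × 9.378 × (0.2781 − 0.0296) = 4.7.
For m = 9: N(4) = 30.9, N(12) = 16.7, and A = 2 × 12.984 × (0.3969 − 0.0787) = 8.3.

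| Median OS | q | k | 12-month OS, SAP rule | True | Bias (points) |
|---|---|---|---|---|---|
| 6.5 | 25% | 1.2 | 26.2% | 27.8% | −1.7 |
| 6.5 | 50% | 2.3 | 24.3% | 27.8% | −3.5 |
| 9 | 25% | 2.1 | 37.3% | 39.7% | −2.4 |
| 9 | 50% | 4.1 | 34.5% | 39.7% | −5.2 |

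(Bias is taken from unrounded values.)

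**6. Simulation over a wider range.** With 4,000 trials per setting, medians of 6, 8 and 10 months, and the last visit at month 3 or 6, the 12-month bias is:
- −0.7 to −1.3 points for q = 10%
- −1.4 to −3.2 points for q = 25%
- −2.9 to −6.6 points for q = 50%
- −6 to −15.5 points for q = 100%

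Censoring at the last date known alive returned the true values to within simulation error in every setting. At 18 months with a median of 6.5 months, a true 15% is estimated as about 12 to 13% for q = 25% and 10 to 11% for q = 50%.

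**7. Scale.** At a rate near 28%, the binomial standard error is √(0.28 × 0.72/42) = 0.069, a 95% half-width of about 14 points. The bias for q = 25% is small beside that, but the confidence interval does not reflect it.

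**The case against.** The strongest reply is that the protocol plans examinations, not telephone calls. The schedule has one every 8 weeks after treatment, and section 7.1 requires follow-up until death. Section 8.2 states the purpose of contact after progression and does not cancel the examination. On the plan as written the bias is negligible, and the larger figures need departures that no passage describes. This stands, and it is why the point is conditional.

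Four further limits also stand:
- The SAP list is not confined to study-site contacts. A family-physician consultation is a medical consultation, and a later anti-cancer treatment can count as a treatment. What is clearly left out is mainly telephone and registry news.
- A patient who misses visits and is not heard of again gets the same date under either rule. The bias needs a patient with no later clinical contact who is nevertheless documented alive.
- A reader might infer a conflict between the protocol's and the SAP's terms for the OS censoring date. Protocol 11.1 itself uses the SAP's term for PFS, so the difference may be one of translation.
- The lack of a stated data cut-off date does not cause the asymmetry. A cut-off is part of a clean rule, not the source of the problem.

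What the reply does not remove is the rule itself. It discards valid evidence of life that the follow-up could produce, and an OS definition should not rely on full attendance after progression in patients aged 70 or over.

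**Conclusion.** The asymmetry is in the stated rule and can act only downward. Its size depends on how survival status is collected after progression, which section 8.2 leaves open. For assumed median OS of 6.5 to 9 months, the 12-month bias is about 0.1 to 0.2 point with full attendance, about 2 points if 25% of patients have only non-visit contact later on, and 3 to 5 points if 50% do. At 18 months it is 0.6 to 0.7 point with full attendance and larger otherwise. The share, the timing of the last visit and the survival distribution are all assumptions.

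A reader might infer that one-year OS will be underestimated, or that the one-year minimum follow-up will go unmet. The documents support neither: both need survival follow-up outside visits, which is not stated. OS is secondary, with no hypothesis or threshold, and the tumour-control decision rule is untouched. The change is worth making because it is cheap, not because the trial's conclusion depends on it.

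**What to change.** In SAP 3.2, give OS and follow-up time their own censoring date: the latest documented date on which the patient was known to be alive, from any source, including telephone and registry. Truncate it at one common data cut-off date, and treat deaths after that date as alive at the cut-off. Update vital status for all patients at the cut-off. Use the same term in Protocol 11.1 and SAP 4.4.1.1.

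Keep a separate PFS censoring date based on disease assessment. A vital-status date would credit patients with progression-free time that nobody had checked.

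The cost is a short SAP change, which SAP 1.6 requires before database freeze, and one vital-status query per surviving patient: about 5 to 8 under the assumptions above.
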